preferences in the videos. Including individuals with mild to moderate cognitive limitations in advance care planning discussions and expressing their EOL preferences is warranted, viable and an ethical approach.^{13,14} Incorporating Me & My Wishes into the care planning process is expected to provide an efficient and effective way for residents to communicate their care preferences for today and at EOL, and to positively influence confidence in communicating preferences and in facilitating documentation of care planning documents.

Our long-term goal is to scale and fully incorporate Me & My Wishes into multiple settings providing long term services and supports. Ultimately, integrating Me & My Wishes videos into the electronic health record or another platform allows for video viewing by multiple individuals and disciplines in various settings. Our short-term goal, and the goal of this proposal, is to conduct Stage II efficacy testing of Me & My Wishes. We will employ a randomized wait-list control design of six nursing homes (48-54 residents). Three nursing homes will be assigned to an early intervention group (residents will share videos initially) and three assigned to the wait-list controls (residents will delay sharing videos). Videos can be viewed two ways: 1) in resident quarterly care conferences; and 2) via a secured web-based link for resident-identified family members. After video viewing, the resident, family and staff can discuss key messages and preferences of the video and add to the care plan.

Specific Aim 1: Examine the efficacy of the Me & My Wishes intervention among a sample of nursing home residents with dementia.

Hypothesis 1: Compared to the waitlist control group (Group 2), the intervention group (Group 1) will have an increase in the proportion of residents with documented goals of care discussions or self-reported conversations about preferences 90 days post video viewing.

Specific Aim 2: Examine self-efficacy of communicating preferences among residents with dementia, informal (family) and formal (staff) caregivers.

Hypothesis 2: Compared to the waitlist control group (Group 2), the intervention group (Group 1) will have greater self-efficacy scores for communicating preferences 90 days post video viewing.

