**National Clinical Trial (NCT) Identified Number: NCT03861429**

**Principal Investigator: [name] NHA**

**Sponsor: University of Utah**

**Grant Number: R21AG058094**

**Funded by: NIA**

**Statistical Analysis Plan**

**August, 1, 2019**

## Randomization

We will employ a randomized wait-list control design with nursing homes and assisted living facilities. We block randomized five nursing homes and three assisted living communities in the Pacific Northwest into two groups based on size, proportion of residents with Medicaid, and proportion of residents with mild to moderate cognitive impairment. In Group 1 (early intervention group) NHs, videorecording, editing, and viewing will occur within three months of baseline. In Group 2 (delayed sharing) NHs, residents will be on a wait-list; after the delayed start, their video will be produced and viewed within three months.

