## Primary & Secondary Outcomes

We will calculate summary statistics for baseline demographics by intervention group, to assess comparability of groups and validate randomization scheme. We will use mixed modeling to compare the outcome measures goals of care discussions and self-efficacy of communicating preferences between Group 1 (early intervention) and Group 2 (wait-list) at 3 time points. Our specific model will be:  $Y = B_0 + B_1X + B_2T + B_3(X \cdot T) + e$  where, Y= goals of care discussions or self-efficacy of communicating preferences, X = Treatment condition (Group 1 vs. Group 2), T = Time point (baseline, 3 months, 6 months). Evaluation of the fixed effect of Treatment condition will tell us whether the two groups differ on average across all time points. The fixed effect of Time will tell us whether goals of care discussions change over time. Evaluation of the interaction of Treatment by Time will tell us if the groups change differentially, and will be the effect of primary interest.

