## Power and Sample Size

Sensitivity analysis was conducted with G-Power 3.1. With a proposed sample size = 48, 2 Groups, 3 timepoints, correlation between time points = .5, power = .90, and alpha = .05, we will be able to detect a medium effect size  $f = .213$  using a general linear modeling of repeated measures looking for within-between subjects' interaction. T= Time point (baseline, 3 months, 6 months).

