## Goals of Care

We analyzed results with an intent to treat approach using SPSS Version 24.0 (SPSS, Armonk, NY). Multilevel logistic regression (generalized estimating equations [GEE] with an autoregressive (1) working correlation matrix, logit link function) were fitted to assess the primary hypotheses. The models account for the repeated measures (3 or 4 time points), correlated, data structure per person. An additive model was conducted with contrast coding for each time point, treatment, and follow-up effects.

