### **Concordance Analysis**

Analyses were conducted using SPSS Version 24.0 (SPSS, Armonk, NY) using an intent to treat approach. Multilevel linear regressions (generalized estimating equations [GEE] with an autoregressive (1) working correlation matrix) were fitted to assess concordance of preferences between the resident videos and staff and family surveys at three (intervention group) or four (wait-list control group) time points. The models account for the repeated measures (three or four time points), correlated, data structure per person. Because this study used a waitlist control design, data includes the initial baseline data for both groups and second baseline data for the waitlist group. An additive model was conducted with contrast coding for each time point, treatment, and follow-up effects. This allowed us to compare the groups by the different times they received the video, with Time 1 (Baseline) as the reference category. For example, a participant in the Immediate group at time of video sharing would receive contrast coding: Time 2 (1); Time 3 (0), Time 4 (0), Treatment (1), Follow-up (0). While a participant in the Wait-list (Control) group at time of video sharing would receive contrast coding: Time 2 (0), Time 3 (1), Time 4 (0), Treatment (1), Follow-up (0). We stratified our analysis by the three different types of participants - residents, family members, and staff members.

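### The .90 power at f = .213 is for a linear group-by-time interaction in independent residents, not for the logistic GEE or the 90-day proportion of Hypothesis 1

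*SAP*

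**What the plan says.** SAP, Power and Sample Size: 48 residents, two groups, three time points, correlation .5, alpha .05 and power .90 give a detectable f of .213, "using a general linear modeling of repeated measures looking for within-between subjects" interaction.

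SAP, Primary & Secondary Outcomes: goals of care discussions and self-efficacy share one linear equation with group, time and their product. On the product term: "Evaluation of the interaction of Treatment by Time will tell us if the groups change differentially, and will be the effect of primary interest".

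SAP, Goals of Care: "Multilevel logistic regression (generalized estimating equations [GEE] with an autoregressive (1) working correlation matrix, logit link function) were fitted to assess the primary hypotheses". This model is additive, with terms for time points, treatment and follow-up, and has no group-by-time product.

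SAP, Concordance Analysis: the same additive model is described with worked codes. Data are collected "at three (intervention group) or four (wait-list control group) time points", and the extra wait-list point is a second baseline. The early group shares at Time 2. A wait-list participant "at time of video sharing would receive contrast coding: Time 2 (0), Time 3 (1), Time 4 (0), Treatment (1), Follow-up (0"). No 90-day row is shown.

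Protocol, Hypothesis 1: the early group is to show an "increase in the proportion of residents with documented goals of care discussions or self-reported conversations about preferences 90 days post video viewing".

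SAP, Randomization: "We block randomized five nursing homes and three assisted living communities in the Pacific Northwest into two groups". For the wait-list, "after the delayed start, their video will be produced and viewed within three months".

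**The concern.** The power statement and the analysis of the primary hypotheses describe different tests. One is a 2-df interaction on a continuous scale with independent residents. The other is a coefficient, or a sum of coefficients, from an additive model for a binary outcome, in residents who came in by randomised facility. Hypothesis 1 also fixes a time, 90 days after viewing, and the wait-list may have been exposed by then.

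Because this is the only power figure, a reader will tend to attach it to Hypothesis 1. A null 90-day result could then be taken as coming from a 90%-powered test. The plan gives no control rate, no detectable percentage-point difference, no 90-day row codes and no named coefficient, so the true figure cannot be worked out from it.

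**Working it through.** **1. The stated figure.** Inputs from Power and Sample Size: N = 48, m = 3, correlation .5, f = .213.

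Lambda = f² × N × m / (1 − correlation) = .213² × 48 × 3 / .5 = 13.07. With df 2 and 92 and alpha .05, power is .8998. The figure reproduces.

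**2. What f = .213 means.** With d_t the standardised group difference at time t, f² = Σ(d_t − mean d)² / 12.
- If the groups differ at one time only, or equally at the last two, d = .213 × √18 = .904 SD.
- If the difference grows linearly, it reaches .213 × √24 = 1.04 SD at the last time.

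**3. Facility clustering on the same test.** Assumed: eight facilities of 48/8 = 6, four per group, with facility-by-time variance c as a share of total variance. The within-resident variance is .5, so lambda is divided by 1 + 5c/.5.

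| c | divisor | lambda | power (df 2, 92) |
|---|---|---|---|
| 1% | 1.10 | 11.88 | .87 |
| 2.5% | 1.25 | 10.45 | .82 |
| 5% | 1.50 | 8.71 | .74 |

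These keep 92 denominator df. Allowing for only eight facilities would lower them further.

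**4. The 90-day effect under the concordance coding.** Two inferences are needed: that this coding also applies to goals of care (both SAP sections describe the additive model in the same terms), and that the early group's third row is Time 3. Columns are intercept, T2, T3, T4, Treatment, Follow-up; x is the unstated Treatment code at 90 days.
- Early: 100000, 110010, 1010x1
- Wait-list: 100000, 110000, 101010, 1001x1

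The matrix has full rank (6) for x = 0 or 1. Only wait-list residents have a Time 4 row, so the Time 4 term absorbs their follow-up. With an AR(1) working correlation of .5, the 90-day effect (Follow-up if x = 0, Treatment + Follow-up if x = 1) has these weights in either case:
- early (−.75, 1, 1); wait-list (.75, −1, −1, 0).

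It is the sum of the Time 2 and Time 3 group differences, less a baseline adjustment. Variance with 24 v 24 (assumed):
- True AR(1): [.5625 + 1 + 1 + 2(−.375 − .1875 + .5)] × 2/24 = 2.4375/12 = .203; SE .451.
- True exchangeable: [2.5625 + 2(−.375 − .375 + .5)] × 2/24 = 2.0625/12 = .172; SE .415.
- Treatment term, either case: SE .250, variance .0625.

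The variance ratio is 3.25 or 2.75.

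**5. Linear-scale power** (two-sided z; same effect, .904 SD, at sharing and 90 days; no missing data).
- Treatment at sharing: .904/.250 = 3.62; power .95.
- 90 days: .904/.451 = 2.00, power .52; .904/.415 = 2.18, power .59.
- Power of .90 at 90 days needs 3.24 × SE = 1.46 or 1.34 SD.
- For comparison, a baseline-to-90-day change against a control still unexposed has power of about .88 at .904 SD.

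**6. Logit-scale power.** A difference of .904 pooled SD is 37 to 41 percentage points over assumed control rates of 10 to 50%. Simulated logistic GEE at +40 points (24 v 24, AR(1) working matrix, latent correlation .7, 2,000 replicates per cell; ranges cover ordinary and bias-corrected sandwich SE and both true correlation structures):

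| control rate | 90-day power |
|---|---|
| 10% | .53–.57 |
| 20% | .43–.49 |
| 30% | .39–.43 |
| 40% | .35–.41 |
| 50% | .30–.36 |

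With the effect matched to .904 SD on the risk-difference or log-odds scale (800 replicates), the span is .30 to .52. The edges are rough: 18–19% of fits failed at 50% in the first set, and 24–49% at 10% in the second.

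**7. Sensitivity.**
- Effect shape, same f, linear scale: .93–.99 if the effect keeps growing to 90 days; .11–.13 if it halves.
- Coding: if the early 90-day row is placed at Time 4, the T4 and Follow-up columns coincide. The rank is 5 of 6 and the 90-day effect is not estimable.

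**The case against.** The power section makes no claim about Hypothesis 1. It is offered as a sensitivity analysis for the interaction that Primary & Secondary Outcomes names as primary, with the same three time points. Those two sections agree, and a linear model suits the self-efficacy scores. This stands: the .90 is neither miscalculated nor unrelated to the plan. But the plan then holds two primary analyses of goals of care, and only one has a power figure.

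A reader might infer that the planned 90-day test of Hypothesis 1 has .5 to .6 power. The documents do not support that, for three reasons:
- The range comes from a continuous-outcome calculation, whereas the plan uses a logit link.
- An omnibus f does not fix a 90-day difference. It takes an assumed shape to get there, and other shapes at the same f run from about .1 to .99.
- The 90-day rows are inferred from sharing rows given under Concordance Analysis.

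Nor do the figures show that .90 power is out of reach. On the logit scale, part of the loss arises because large effects push the treated proportion towards 85 to 90%, where the Wald test weakens and fits fail. In a further simulation at a 10% control rate, +60 points gave about .81.

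The clustering figures also rest on an assumed variance share and equal facilities. They show direction and plausible size, not an estimate for this trial.

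**Conclusion.** The concern holds in limited form, with moderate confidence. Two parts need no assumption. The .90 at f = .213 is correct only for the linear 2-df interaction in 48 independent residents. The SAP gives no power for the logistic GEE or for a 90-day proportion, and makes no allowance for randomised facilities.

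The sizes are conditional. Clustering takes the .90 to about .87 to .74 for an assumed facility-by-time share of 1 to 5%, before any few-cluster penalty. If the concordance coding applies, the early 90-day row is Time 3, allocation is 24 v 24, the correlation is .5 and the effect is equal at sharing and 90 days, power for the 90-day effect is about .52 to .59 on the linear scale and mostly about .3 to .55 on the logit scale. They illustrate how far the GEE contrast can fall below .90. They are not the trial's power for Hypothesis 1, which the plan leaves undetermined.

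**What to change.** - In Power and Sample Size, say that .90 at f = .213 applies to the linear group-by-time interaction with independent residents, give its size (about .90 SD for a step, 1.04 SD if linear), and do not present it as power for Hypothesis 1.
- Reconcile the linear equation in Primary & Secondary Outcomes with Goals of Care, so that goals of care has one primary analysis with a logit link.
- Name the coefficient, or sum of coefficients, that tests Hypothesis 1. State the Time, Treatment and Follow-up codes of the 90-day rows in both groups, and confirm that they make the contrast estimable.
- Restate the detectable percentage-point difference for that contrast over stated control rates, resident allocation and facility ICCs.

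The cost is SAP wording and one recalculation. The stated figure will be less favourable. No participants are added.

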## Goals of Care

We analyzed results with an intent to treat approach using SPSS Version 24.0 (SPSS, Armonk, NY). Multilevel logistic regression (generalized estimating equations [GEE] with an autoregressive (1) working correlation matrix, logit link function) were fitted to assess the primary hypotheses. The models account for the repeated measures (3 or 4 time points), correlated, data structure per person. An additive model was conducted with contrast coding for each time point, treatment, and follow-up effects.

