Hypothesis 3: Compared to the waitlist control group (Group 2), the intervention group (Group 1), the proportion of residents with documented new or changed care planning documents (e.g. advance directive) will increase by 90 days post video viewing.

Specific Aim 3: Describe congruence of preferences observed in the Me & My Wishes video, care conference audio recording, medical record (e.g. POLST), and in family and staff surveys.

PROCEDURES

Training Checklist for Research Staff

Orientation to Project

- CITI/GCP Trainings
- Read: [name] (2015) and [name] (2017) Articles
- Review: R21 Research Plan
- Read: Training Manual Introduction
- ID Badge
- UBox
- IRB (ERIC)
- Encryption
- Skype for Business

Recruitment/Enrollment

- Review Documents: Eligibility Checklist, Demographic & Clinical Information, Consents
- Practice approaching residents and describing the study
- Practice consenting process
- Practice approaching NH staff and families to describe the study
- Practice contacting family/friends via telephone (consent and survey procedures)
- Create a Tickler System/Calendar for MMW video recording, care conference and follow ups

Video Production

- Practice facilitating the Conversation Guide
- Video Recording and Equipment
- Video Editing (see detailed process on page X)

Data Collection & Management

Cloud Storage

- REDCap: Orientation, Survey Entry and Data Management
- Data Security: Information Storage and Confidentiality
- REDCap participant tracking (enrollment, refusals, withdraws)
- Participant Tracking: IDs, Calendar, Study Enrollment

Nursing Facility (Site)

- Discuss how to perform the Chart Review
- Practice administering the Resident Surveys (baseline, time of sharing, 90 days)
- Discuss the logistics of administering the Staff and Family surveys in care conference
- Discuss how to set up Care Conference Audio Recording and Equipment
- Practice administering Staff and family surveys (baseline, time of sharing, 90 days)

Data Analysis

- Audio Transcription and verification
- REDCap – how to run reports (e.g. accrual reports)
- NVivo – (e.g. uploading documents, coding)

Chapter Three

Eligibility, Recruitment and Enrollment

Eligibility Criteria

Use the Eligibility Checklist (Appendix A) to document whether selected residents are eligible to participate in this study or not.

❖ Resident Inclusion Criteria

We will include assisted living (AL) residents in addition to nursing home (NH) residents. Inclusion criteria:

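### The SAP names no primary hypothesis and gives no multiplicity rule; if each test is run at .05, family-wise error runs from 5% to at most about 23%, depending on how the text is read

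*SAP*

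**What the plan says.** **Protocol, Chapter Two.** There are three directional hypotheses.
- Hypothesis 1 (H1) belongs to Aim 1, the only aim worded in terms of efficacy. It concerns the proportion of residents with a recorded or self-reported conversation about preferences by 90 days after viewing.
- Hypothesis 2 (H2) concerns self-efficacy scores. Its parent, Aim 2, is to "Examine self-efficacy of communicating preferences among residents with dementia, informal (family) and formal (staff) caregivers".
- Hypothesis 3 (H3), also listed under Aim 2, concerns the proportion of residents with new or amended care planning documents.
- Aim 3 carries no hypothesis. It is to "Describe congruence of preferences observed in the Me & My Wishes video, care conference audio recording, medical record", among other sources.

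**SAP, Primary & Secondary Outcomes.** The heading implies a ranking, but the text assigns no outcome to either class. One mixed model serves both goals of care and self-efficacy, and the treatment-by-time interaction is named as the effect that matters most for both.

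**SAP, Goals of Care.** Logistic GEE models "were fitted to assess the primary hypotheses". The hypotheses are not listed. The model is additive, with separate contrasts for time, treatment and follow-up.

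**SAP, Power and Sample Size.** "With a proposed sample size = 48, 2 Groups, 3 timepoints, correlation between time points = .5", then "power = .90, and alpha = .05", giving a detectable f of .213 when "looking for within-between subjects' interaction". This is the only place where alpha is stated.

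**SAP, Concordance Analysis.** Linear GEE models use the same kind of contrasts, and "We stratified our analysis by the three different types of participants - residents, family members, and staff members".

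**The concern.** The Protocol presents the trial as Stage II efficacy testing, so the plan should say which result decides efficacy. It does not. Someone following the SAP as written has two outcomes of equal standing, an unlisted set of primary hypotheses and one alpha that is tied to none of them. A positive result on any one outcome could be presented as the trial's success, and a reader could not tell what error rate stands behind that claim.

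The gap extends to H1 itself. The interaction in the mixed model and the treatment and follow-up effects in the additive GEE are different tests of the same outcome. Naming the outcome alone would still leave a choice of test.

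**Working it through.** **1. Reproduce the plan's own figure.** Inputs from SAP, Power and Sample Size: N = 48, 2 groups, m = 3 time points, correlation ρ = .5, alpha = .05, power = .90. For the within-between interaction with no sphericity correction:
- noncentrality λ = f² × N × m / (1 − ρ) = .213² × 48 × 3 / .5 = 13.07
- df1 = (2 − 1)(3 − 1) = 2 and df2 = (48 − 2)(3 − 1) = 92
- power from the noncentral F at f = .213 is .8998, and the f that gives power .90 is .2131

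The stated f = .213 is reproduced. It is the detectable effect for one test at an undivided .05.

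**2. Family-wise error by reading.** For k independent tests, each at .05 with every null true, the chance of at least one rejection is 1 − .95^k.

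| Reading of the text | k | Family-wise error |
|---|---|---|
| H1 is the sole primary | 1 | 5.0% |
| The two outcomes in SAP, Primary & Secondary Outcomes | 2 | 1 − .9025 = 9.75% |
| H1, H2, H3, one test each | 3 | 1 − .8574 = 14.3% |
| H1 plus H2 in residents, family and staff | 4 | 1 − .8145 = 18.5% |
| As above, plus H3 | 5 | 1 − .7738 = 22.6% |

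**3. Allow for correlation.** The outcomes come from the same residents and from linked family and staff, so positive correlation is likely. The documents give no value, so a range is assumed. Simulation of equally correlated two-sided z-tests (1,000,000 draws, all nulls true) gives:

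| k | r = .3 | r = .5 | r = .7 |
|---|---|---|---|
| 3 | 13.6% | 12.5% | 11.0% |
| 4 | 17.5% | 15.6% | 13.0% |
| 5 | 20.9% | 18.4% | 14.9% |

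**4. Price the alternatives.** Bonferroni over five tests sets alpha at .05 / 5 = .01. In the noncentral F of step 1, power at f = .213 falls from .90 to .741, and the f detectable with 90% power rises from .213 to .252. Over two tests (alpha .025), power is .839 and detectable f is .231. One named primary test keeps alpha at .05, so the stated power is unchanged.

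**The case against.** The strongest reply is that the high figures rest on a list of tests that the plan does not contain. Much of this stands.

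- A reader might infer that five primary hypotheses are each tested at .05. The documents do not say so: alpha appears once, in a sensitivity calculation for one interaction.
- The sentence about primary hypotheses sits under Goals of Care and describes a logistic model. That suits goals of care and, at most, H3. It does not suit self-efficacy scores. Read narrowly, it gives 5% to 9.75%.
- The SAP names no analysis for H3. It states stratification by participant type only for concordance, so three self-efficacy tests are an inference from Aim 2.
- Singling out the interaction ranks coefficients within a model, not outcomes. The section heading suggests that some outcomes are secondary.
- A reader might add three concordance tests and reach 1 − .95^8 = 33.7%. Concordance does get treatment contrasts, but nothing calls them primary or efficacy tests, and Aim 3 is descriptive.
- No rule says that one positive result counts as success. That possibility arises from silence.

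What the reply does not remove is the gap itself. No outcome is designated primary, two outcomes are handled identically, and no multiplicity rule exists. Even the two-outcome reading, which comes straight from the SAP, nearly doubles .05 if each outcome is tested at that level.

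**Conclusion.** The concern holds as a failure to designate. The SAP does not identify the primary hypothesis and does not control multiplicity. A flat statement that the error rate is 18% to 23%, or about four times alpha, is not supported, because it takes the largest test counts as the plan's own and leaves out stronger correlation. The supportable size is the range in the first table: 5% with one primary, about 10% for the two outcomes the SAP models together, and about 23% as the ceiling for five tests.

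These figures assume that each test is run at .05 and holds that level, that all nulls are true, and that any single positive result would be claimed as efficacy. The values below the independence figures also depend on assumed correlations. The ambiguity affects what may be claimed, not whether the trial can be run.

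**What to change.** - In SAP, Primary & Secondary Outcomes and Goals of Care, state that H1 (goals of care, in residents) is the single primary test at two-sided .05. It is the natural choice: Aim 1 is the efficacy aim, and the reference to primary hypotheses sits under Goals of Care.
- Name the one model, coefficient and time point that decide H1. Without this, 5% is not secured.
- Label H2 (residents, family, staff) and H3 secondary. Either treat them as supportive only, or test them under Holm at .05 after a positive H1. With four such tests, the first Holm step is .05 / 4 = .0125. Add the missing analysis for H3.
- Report concordance as estimates with intervals and no efficacy claim, in line with Aim 3.
- Date the designation. The SAP is dated August 2019, but the Goals of Care and Concordance Analysis sections are written in the past tense. If the analyses had already been run, disclose the designation as post hoc.

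This is a change of wording only: it needs no new data and takes no alpha from H1. The downside is that a lone positive secondary result becomes supportive rather than confirmatory.

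### For goals of care, the SAP ties two different analyses to the primary question and gives no rule for which one decides

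*SAP*

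**What the plan says.** The SAP describes the analysis of goals of care discussions twice.

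- **Primary & Secondary Outcomes.** In the future tense: "We will use mixed modeling to compare the outcome measures goals of care discussions and self-efficacy of communicating preferences". The equation has a group term, a time term and their product, with time at baseline, 3 months and 6 months. On which term matters: "Evaluation of the interaction of Treatment by Time will tell us if the groups change differentially, and will be the effect of primary interest".
- **Goals of Care.** In the past tense: "We analyzed results with an intent to treat approach". Logistic GEE models with an AR(1) working correlation, over three or four time points per person, "were fitted to assess the primary hypotheses". On their form: "An additive model was conducted with contrast coding for each time point, treatment, and follow-up effects". No coefficient is singled out.

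The only alpha and power are under Power and Sample Size. They come from a calculation "using a general linear modeling of repeated measures looking for within-between subjects' interaction".

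Hypothesis 1 in the protocol concerns the proportion of residents with a documented discussion or a self-reported conversation, compared between groups 90 days after viewing. The outcome is therefore binary and the comparison is at one follow-up time.

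**The concern.** Both sections claim the primary question for the same outcome, but they describe different tests. They differ in link function, in the number of visits used and in the terms estimated. The first names its decisive effect. The second offers at least a Treatment and a Follow-up coefficient and does not choose between them. Neither section calls the other a sensitivity analysis, a replacement or a refinement, and the SAP has no multiplicity rule.

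A positive result on any of these tests could therefore be presented as the primary finding without departing from the SAP as written. Preventing that is a main purpose of an SAP. At stake are the error rate attached to Hypothesis 1 and whether a reader can tell which result answers it.

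**Working it through.** **1. The plan's own figure.** Inputs from Power and Sample Size: "With a proposed sample size = 48, 2 Groups, 3 timepoints" and "correlation between time points = .5, power = .90, and alpha = .05". For a repeated-measures within-between interaction with k = 2 groups and m = 3 time points:

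- noncentrality = f² × N × m / (1 − rho) = .213² × 48 × 3 / .5 = .045369 × 288 = 13.07
- df1 = (k − 1)(m − 1) = 2; df2 = (N − k)(m − 1) = 92
- power at alpha .05 = .8998; the f giving exactly .90 is .2131

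The stated f = .213 reproduces. The stated alpha and power therefore belong to the interaction, in a model for a continuous outcome. No alpha or power is stated for the GEE.

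**2. Bounds when any one of several 5% tests may be called primary.**

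- Two tests: 1 − .95² = 9.75% if independent; ceiling 2 × 5% = 10%.
- Three tests: 1 − .95³ = 14.3% if independent; ceiling 3 × 5% = 15%.

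**3. Rates allowing for the overlap between tests.** The tests share data, so the true rates fall below the independent values. They were simulated under no effect, with these assumptions:

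- 24 residents per group (the documents give no split) and no facility clustering;
- Group 1 seen three times and Group 2 four times;
- the contrast coding given under Concordance Analysis applied to goals of care. That coding sets Treatment to 1 at video sharing in each group. It does not show Treatment's value at follow-up, so both 0 and 1 were tried;
- AR(1) or exchangeable correlation, with 400,000 Gaussian draws per setting.

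The SAP does not say whether time enters the interaction as categorical (2 df) or linear (1 df), so both are shown. At the SAP's correlation of .5:

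| Trial called positive if significant on | Time categorical | Time linear |
|---|---|---|
| Interaction, or GEE Treatment | 8.1-8.2% | 9.4-9.6% |
| Interaction, or one joint test of Treatment and Follow-up | 7.0-7.3% | 8.6-8.9% |
| Interaction, Treatment, or Follow-up | 10.1-11.5% | 11.0-12.6% |

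Over correlations from .1 to .9 the two-test rates run from 6.0% to 9.7% and the three-test rates from 9.1% to 13.0%.

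**4. Check with a binary outcome.** Logistic GEEs were fitted to about 3,000 null trials per setting (event rate .4, an assumption; correlations .3, .5 and .7). With each test calibrated to 5%, interaction or Treatment gave 7.6-9.7%, and any of the three gave 10.8-12.9%. Uncalibrated, the rates were 8.0-10.3% and 11.9-13.2%. The excess over 10% arises because some single tests ran above 5% in samples this small.

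**5. With one test named in advance,** the nominal rate is 5%. If both were kept as co-primary at .025 each, the rate would be at most .025 + .025 = 5%.

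**The case against.** The best defence is that the two sections are less opposed than they look. The logit link suits a binary outcome, whereas the mixed-model equation has an additive error and also serves the self-efficacy scores. The GEE could therefore be the outcome-specific form of the general plan. Under the Concordance Analysis coding, Treatment also varies with time: at Time 2 it is 1 in Group 1 and 0 in Group 2. The additive model thus contains a constrained group-by-time contrast, although it has no product term. Both observations stand. They do not settle which test decides, because the SAP never states the link between the sections and the GEE names no coefficient.

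Four stronger readings are tempting, and the documents do not support them.

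- **That the plan's error rate is already inflated.** The SAP nowhere says that any significant test makes the trial positive. The inflation is conditional on that use.
- **That two competing tests give 12%.** Two 5% tests cannot exceed 10%. Higher rates need Treatment and Follow-up to count separately, and the SAP does not say that they do.
- **That the GEE was chosen after seeing results.** The SAP carries one date, 1 August 2019. The past tense raises the question, but the documents do not show when the section was written or when outcomes were seen.
- **That the analyses would often contradict each other.** With an effect only at 90 days and correlation .5, the interaction and the Treatment coefficient disagreed in about 46-47% of simulated trials. But Treatment then estimates the effect at sharing, and Follow-up carries the 90-day effect. Against a joint test of both coefficients, disagreement was 18-19%.

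**Conclusion.** The concern holds as an unreconciled pair of primary analyses. It goes beyond missing detail, because the two sections as written give different rules for the same hypothesis. If either analysis may be declared primary, the false-positive rate is about 7-10% instead of 5%. It is about 10-13% if Treatment and Follow-up can each count. These ranges rest on the 24:24 split, no facility clustering, and the Concordance Analysis coding carried over to goals of care. The conflict in the text needs none of these assumptions.

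The conflict should not be settled by keeping the interaction merely because it has a stated alpha and power. That power is for a continuous outcome, and an overall interaction across three time points does not isolate the 90-day comparison in Hypothesis 1.

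**What to change.** In the SAP's Primary & Secondary Outcomes and Goals of Care sections:

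1. Name one model and one contrast as the decisive test of Hypothesis 1 at two-sided .05. It should suit a binary outcome and match the 90-day comparison.
2. Label the other model and all remaining coefficients supportive, with no claim of efficacy resting on them.
3. Write out the contrast coding for goals of care, including the value of Treatment at follow-up.
4. If the GEE replaced the interaction, say so, give the date and reason relative to data access, and report the interaction beside it.
5. State that the alpha and power under Power and Sample Size apply only to the interaction.

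This needs wording only and no new data. The small downside is that a positive result on a non-designated test can no longer be reported as primary. If outcomes have already been analysed, naming a test now is itself a post hoc choice. Item 4 therefore matters most in that case, and both results should be shown.
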